#### 4.3.3.1.3 INDEPENDENT PHOTOGRAPHIC REVIEW TRAINING PROCESS

IPR assessors will participate in a training session prior to completing the IPR. The purpose of the training is to provide guidance to the IPR assessors on the methods for reviewing the study images and to provide sample images for scoring and discussion of the scoring by IPR assessors. Instructions will include that each blinded assessor should pay close attention to changes in overall appearance of lift in the treatment area.

#### 4.3.3.2 GLOBAL AESTHETIC IMPROVEMENT SCALE (GAIS)

The Global Aesthetic Improvement Scale (GAIS) is a 5-point scale that rates global aesthetic improvement from the pretreatment appearance. In this study, both live observation and photo review are utilized by the physician or a qualified, delegated clinician and subject in order to assign a score. The CGAIS must be performed by the principal investigator, sub-investigator or qualified clinician delegated by the principal investigator. Both the CGAIS and SGAIS should be completed in two steps:

- Based on a live assessment of the subject while referring to the subject's pre-treatment photographs (subjects should be given a hand mirror for assessment); and
- Based on a comparison of the subject's pre-treatment photographs to the current post-treatment photographs.

The Investigator will grade the overall improvement of treatment area as indicated in **Table 3** by comparing the subject's appearance at follow-up visits against a photograph taken prior to procedure. Likewise, the subject will also rate their improvement compared to pre-treatment as shown in **Table 4**. The GAIS results will be collected at the 30-day, 90-day and 180-day follow-up visits.

Rating	Description
Very much improved	Optimal cosmetic result from this procedure in this subject
Much improved	Marked improvement in appearance from the initial condition, but not completely optimal for this subject
Improved	Obvious improvement in appearance from the initial condition
No change	The appearance is essentially the same as the original condition
Worse	The appearance is worse than the original condition
Much worse	The appearance is much worse than the original condition
Very much worse	The appearance is very much worse than the original condition

#### TABLE 3: GLOBAL AESTHETIC IMPROVEMENT SCALE EVALUATION - INVESTIGATOR

MEDICAL Apyx Medical Corporation	
Protocol Number: APX-22-03	Effective Date: 23SEP2022
	Revision No: 2.0
Title: Minimally Invasive Breast Lift Procedure Utilizing the Renuvion APR System	

#### TABLE 4: GLOBAL AESTHETIC IMPROVEMENT SCALE EVALUATION - SUBJECT

Rating	
Very much improved	
Much improved	
Improved	
No change	
Worse	
Much worse	
Very much worse	

#### 4.3.3.3 PATIENT SATISFACTION SURVEY (PSQ)

The study subjects will be asked to complete a Patient Satisfaction Survey, see **Appendix A**, at the 180-day follow-up visit.

#### 4.3.3.4 BREAST-Q

The study subjects will be asked to complete a Breast-Q, see **Appendix B**, at the Baseline (pre-procedure) and 180day follow-up visits. The Breast-Q Version 2.0 Augmentation Module Pre- and Postoperative Scales have been provided for use under license from Memorial Sloan Kettering Cancer Center. Subjects will complete the Psychosocial Well-Being and Sexual Well-Being questionnaires.

#### 4.3.3.5 NUMERIC RATING SCALE (NRS)

The study subjects will be asked to complete a 11-point Numeric Rating Scale (NRS) for the level of pain and discomfort associated with the study procedure – to be completed by the subjects on the day of the procedure prior to the procedure, following the procedure, and at all follow-up visits. The average pain score for the entire region treated will be recorded. Directions to subject will be: "Please rate the average pain you are experiencing in the treatment area on a scale of 0-10, with 0 being 'Best/No Pain' and 10 being the 'Worst Possible Pain'."

Pain will be defined in this study as the average pain reported in the treatment area using the following categories: None (Score of 0), Mild (Score of 1-5), Moderate (Score of 6-7), and Severe (Score of 8-10). Classifications of NRS pain scores have been documented in literature. Moderate and severe pain/discomfort are considered Adverse Events (AE). Severe subject reported pain does not necessarily correlate to a "severe" adverse event classification. Events will be classified by investigator based on clinical evaluation, the effect to daily activities, and mitigation needed as per **Section 8** of this protocol.

Subjects experiencing pain adverse events will be considered resolved when their pain score is documented as returning to a 0 score. The NRS will be completed pre-treatment, post-treatment, daily in the subject diary, and at all follow-up visits to capture pain scores.

MEDICAL Apyx Medical Corporation	
Protocol Number: APX-22-03	Effective Date: 23SEP2022 Revision No: 2.0

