#### 2.2 POTENTIAL RISKS AND BENEFITS

#### 2.2.1 POTENTIAL RISKS

This treatment modality was designed to inherently minimize the risk to the subject. However, treatment with energy-based modalities (laser, radiofrequency, and plasma devices) produce subsequent heating of the soft tissue that could involve the following commonly Expected Treatment Effects (ETEs): discomfort/pain, edema, erythema, ecchymosis, hypoesthesia, temporary sensory nerve injury (touch sensitivity, itching, temporary numbness/tingling), transient migratory firmness, and temporary and/or transient crepitus.

In addition to commonly expected treatment effects, treatment with the Renuvion APR device could involve the following risks: helium embolism into the surgical site due to inadvertent introduction into the venous or arterial blood supply system, unintended burns (deep or superficial), pneumothorax, temporary or permanent motor nerve injury, ischemia, fibrosis, infection, gas buildup, bleeding, hematoma, seroma, subcutaneous induration, pigmentation changes, increased healing time, unsatisfactory scarring, asymmetry and/or unacceptable cosmetic result.

Risks associated with tumescent anesthesia (lidocaine and epinephrine) include blurred vision, mental/mood changes, drowsiness, dizziness, unusually slow heartbeat, rash, itching, swelling, anxiety, apprehensiveness, restlessness, tremor, weakness, sweating, palpitations, pallor, nausea and vomiting, headache, and respiratory difficulties.

Subjects using drugs that reduce coagulation (aspirin or NSAIDs) may experience increased bruising or bleeding at the treatment site. Any other medication prescribed for the procedure or after-procedure by the investigator have their own risks; these risks should be discussed with the subject.

A grounding pad is used to ground/neutralize the electrical current. Subjects undergoing radiofrequency treatment will be kept away from contact with metal parts which are grounded, or which have appreciable capacitance to earth.

Any unexpected or unforeseen complications will be managed by the investigator throughout the conduct of the study. Unforeseen or unexpected side effects not listed above will be reported to the sponsor and regulatory representatives (Ethics Committee) as they occur.

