#### 4.3.2 SAFETY ENDPOINTS

- 1. Analysis of adverse events through the D180 post-treatment visit.
- During study treatment, the subject's pain levels will be monitored using the 11-point Numeric Rating Scale (NRS). The average pain score for the entire region treated will be recorded. Pain scores will be recorded at all follow-up visits.

MEDICAL Appx Medical Corporation	
Protocol Number: APX-22-03	Effective Date: 23SEP2022 Revision No: 2.0
Title: Minimally Invasive Breast Lift Procedure Litilizing the Renuvion APR System	

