#### Title: Minimally Invasive Breast Lift Procedure Utilizing the Renuvion APR System

#### 4.3.3.6 Adverse Event Reporting

The definitions of Adverse Events (AEs) and the subtypes are provided in Section 8 of the study protocol. Adverse events will be classified by the investigator as to:

- Anticipated vs unanticipated
- Serious vs not serious
- Expected Treatment Effect (ETE) vs Adverse Event (AE)
- Severity: mild, moderate, severe
- Device causality: not related, related, undetermined
- Procedure causality: not related, related, undetermined.

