### 8. ASSESSMENT OF SAFETY

#### 8.1 Specifications of Safety Parameters

#### 8.1.1 DEFINITION OF AN EXPECTED TREATMENT EFFECT (ETE) AND AN ADVERSE EVENT (AE)

An expected treatment effect is defined as any typical treatment side-effect of Renuvion APR System of mild to moderate severity and lasting up to a typical maximum duration. An adverse event is defined as any new medical problem, or exacerbation of an existing problem, experienced by a subject while enrolled in the study, whether or not it is considered device-related by the investigator.

A preexisting condition (one that is present at the start of the study) will be recorded as an AE only if the frequency, intensity, or the character of the condition worsens during the study period. Neither the condition, hospitalization, prolonged hospitalization, nor surgery are reported as an AE in the following circumstances: hospitalization or prolonged hospitalization for diagnostic or elective surgical procedures for a preexisting condition. Surgery should not be reported as an outcome of an AE if the purpose of the surgery was elective or diagnostic and the outcome was uneventful.

All ETEs and AEs will be collected during the conduct of this trial.

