#### 8.2 CLASSIFICATION OF AN EVENT

#### 8.2.1 SEVERITY OF EVENT

Each adverse event should be assessed for its severity, or the intensity of an event experienced by the subject, using the following classifications:

- **Mild:** easily tolerated by the subject, causing minimal discomfort, and not interfering with everyday activities. These events generally do not require treatment.
- **Moderate:** sufficiently discomforting to interfere with normal everyday activities. These events are usually relieved by simple therapeutic measures.
- **Severe:** prevents normal, everyday activities. These events may require systemic drug therapy or other medical treatment.

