#### 8.3 TIME PERIOD AND FREQUENCY FOR EVENT ASSESSMENT AND FOLLOW-UP

The occurrence of an AE or SAE may come to the attention of study personnel during a study visit or upon review by a study monitor. All ETEs and AEs will be captured on the appropriate CRF. Information to be collected includes event description, date of onset, clinician's assessment of seriousness and severity, relationship to study device/treatment (assessed only by those with the training and authority to make a determination), actions taken, and date of event resolution. All AEs occurring while on study must be documented appropriately regardless of relationship. All ETEs/AEs assessed as "not yet resolved" must continue to be followed via telephone contact, email or clinic visit every 30 days or sooner as per the physician's direction until event resolution or stabilization.

A pre-existing condition should not be reported as an adverse event unless there has been a substantial increase in severity or frequency of the problem that has not been attributed to natural history. Changes in the severity of an event will be documented to allow for a determination if the event should be re-categorized from an ETE to AE.

Safety evaluations for this study include an interview with the study subject at each follow-up visit by the Investigator or delegated study staff to elicit information about any medical occurrence that meets the definition of Adverse Event. This information will be documented in CRF without regard for cause or relation to device and/or procedure.

In addition, study subjects will be instructed in the Informed Consent Form, post-procedure take-home instructions, and verbally by study staff to report all complications experienced post study procedure to the site personnel as soon as they occur/are observed. Study staff will ensure that monitoring and management of all adverse events is prioritized.

Study investigators are provided liberty to mitigate adverse events as deemed necessary per IHC GCP Guidelines E6(R2)4.3.2 which states, "During and following a subject's participation in a trial, the investigator/institution should ensure that adequate medical care is provided to a subject for any adverse events related to the trial".

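### Does the plan leave open whether pain scored 6 or 7 is an adverse event or an expected treatment effect?

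*Combined protocol and SAP*

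**What the plan says.** Five parts of the combined protocol and SAP bear on the label given to post-procedure pain.

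- **Section 4.3.3.5 (NRS)** sets four bands: 0 none, 1 to 5 mild, 6 to 7 moderate, 8 to 10 severe. It then states "Moderate and severe pain/discomfort are considered Adverse Events (AE", with no exception for pain that was to be expected. It adds that pain scored as severe need not be an event graded severe, and continues: "Events will be classified by investigator based on clinical evaluation, the effect to daily activities, and mitigation needed as per" (the reference is to Section 8).
- **Section 8.1.1** defines an ETE as "any typical treatment side-effect of Renuvion APR System of mild to moderate severity and lasting up to a typical maximum duration". It puts no figure on that duration.
- **Section 2.2.1** opens its list with "commonly Expected Treatment Effects (ETEs): discomfort/pain, edema, erythema" and attaches no severity limit to pain.
- **Section 4.3.3.6** includes "Expected Treatment Effect (ETE) vs Adverse Event (AE" among the classifications the investigator makes.
- **Section 8.3** covers events that become milder or worse: "severity of an event will be documented to allow for a determination if the event should be re-categorized from an ETE to AE".

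The first safety endpoint in Section 4.3.2 is "Analysis of adverse events through the D180 post-treatment visit". The pain score is the second. Section 10.1 plans descriptive statistics only, and Section 10.2 allows up to 15 treated subjects.

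**The concern.** Take a subject who reports a 6 or 7 after the procedure. Under Section 4.3.3.5 this is an AE. Under Section 8.1.1, read with Section 2.2.1, it could be called a typical effect of moderate severity, and so an ETE. Section 4.3.3.6 leaves the label to the investigator. None of these sections says that one yields to another.

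The word *moderate* adds to the doubt. In Section 4.3.3.5 it is a score band. In Section 8.2.1 it is a functional grade, "sufficiently discomforting to interfere with normal everyday activities". The two scales are not mapped to each other.

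At stake is the AE count, which feeds the first safety endpoint. In a study this small, a few relabelled pain events would visibly change the percentage of subjects with an AE. If the choice were made after the data were seen, a reader might not know which rule had been used.

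**Working it through.** The plan states no expected AE rate and no expected frequency of moderate pain, so there is no figure to reproduce. The check sets the sections side by side and then sizes the consequence.

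**Step 1: two candidate readings**

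- Reading A: pain scored 1 to 5 may be an ETE; pain scored 6 to 10 is an AE.
- Reading B: typical pain scored 6 or 7 may be recorded as an ETE.

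**Step 2: each reading against each section**

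| Section | Reading A | Reading B |
|---|---|---|
| 2.2.1, pain in the list of expected effects | Met: mild pain is the listed effect, and the list sets no scoring rule | Met |
| 4.3.3.5, pain rule | Met | Not met: a 6 or 7 is an AE there |
| 4.3.3.6, investigator decides ETE or AE | Met: judgement remains for scores 1 to 5 and for every effect other than pain | Met |
| 8.1.1, ETE and AE definitions | Met: the ETE definition covers only typical effects, and the AE definition is broad enough to take in new pain at any score | Met |
| 8.3, move from ETE to AE as severity changes | Met: for pain, Section 4.3.3.5 supplies the threshold | Met, but no threshold is available |

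Reading A satisfies all five. Reading B fails the only sentence that addresses pain by score. Reading a specific rule inside a general definition is ordinary practice.

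**Step 3: the two meanings of moderate**

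Section 4.3.3.5 defines the band in the same paragraph as the AE rule, so within that rule the word means a score of 6 or 7. The pointer to Section 8 follows a remark that a severe score is not the same as a severe event. Its natural subject is the severity grade given to an event. The score decides whether pain is an AE, and Section 8.2.1 decides how that AE is graded.

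**Step 4: size**

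- Disputed scores: 6 and 7, which is 2 of the 11 points on the scale. Scores of 8 to 10 could join them only if the investigator graded the event below severe and Section 4.3.3.5 were again set aside.
- Treated subjects: 15 (Section 10.2).
- Let k be the number of subjects whose only event is pain of this kind. The shift in the share of subjects with an AE is k/15.
- For k = 1: 1/15 = 0.0667, or 6.7 percentage points.
- The documents do not give k. The arithmetic limits are 0/15 = 0 and 15/15 = 100 points, so no total can be claimed.

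**Step 5: what would be lost**

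Nothing would be lost from the record. Section 8.1.1 has both ETEs and AEs recorded, and Section 8.3 has unresolved events of either kind followed. The pain score is captured whichever label is used. An event graded severe falls outside the ETE definition under either reading, so the trigger in Section 8.5 based on severe device-related AEs is unaffected.

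**The case for a change.** The strongest contrary case is that Reading A, however sensible, is not written down. Section 4.3.3.5 itself sends classification to Section 8, and Section 8 contains the ETE definition that reaches moderate effects. Someone could argue in good faith that the general definition was meant to govern. Section 8.3 gives no threshold of its own, the typical maximum duration has no figure, and Section 10.1 offers no analysis rule that would settle the matter later. The label also has a side effect: Section 4.3.3.5 closes a pain AE only when the score returns to 0, and it states no such criterion for a pain ETE.

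Part of this stands. The protocol does not state how the two definitions fit together, and *moderate* does carry two meanings. It does not stand that both readings follow the protocol equally, because Reading B has to disregard an explicit sentence. The closing rule affects the recorded duration of an event, but not whether the event or its scores are captured.

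One could ask for an extra table of all pain events by highest score band, or for the AE rate with and without pain. Either would be informative. Both are reporting preferences, and neither corrects a wrong result.

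**Conclusion.** No change to the plan is needed. The tension in wording is real, but following Section 4.3.3.5 as written gives a sound descriptive account of pain and contradicts none of the other sections. An analyst who tabulates pain scored 6 to 10 as AEs, and says so in a table footnote, has filled the gap properly.

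Any departure from that would change only the heading under which some pain events appear. The size is 6.7 percentage points in the subject-level AE share for each affected subject with no other AE, assuming all 15 are treated. The number of such subjects is unknown. The conclusion rests on three features of the plan: ETEs and AEs are both recorded, pain scores are a safety endpoint in their own right, and no hypothesis or threshold is attached to the AE rate. A clarifying sentence from the sponsor would do no harm, but no result depends on it.

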#### Title: Minimally Invasive Breast Lift Procedure Utilizing the Renuvion APR System

#### 4.3.3.6 Adverse Event Reporting

The definitions of Adverse Events (AEs) and the subtypes are provided in Section 8 of the study protocol. Adverse events will be classified by the investigator as to:

- Anticipated vs unanticipated
- Serious vs not serious
- Expected Treatment Effect (ETE) vs Adverse Event (AE)
- Severity: mild, moderate, severe
- Device causality: not related, related, undetermined
- Procedure causality: not related, related, undetermined.

#### 4.3.3.7 PTOSIS CLASSIFICATION

The Rainbow Scale for breast ptosis is validated for photographic review of the anterior-posterior view, the lateral view, and the oblique view, see **Figure 3**, **Figure 4**, and **Figure 5**, using the following grades at baseline at D180:

- Grade I (no breast ptosis): thoraco-mammary angle >90°, no visible breast ptosis.
- Grade II (mild breast ptosis): thoraco-mammary angle <90°, but nipple lies still above the level of the inframammary fold.
- Grade III (moderate breast ptosis): the nipple lies at the level of the inframammary fold, above the inferior breast contour.
- **Grade IV (severe breast ptosis)**: the nipples below the level of the inframammary fold but remains above the inferior breast contour.
- Grade V (extreme breast ptosis): the nipple lies below the level of the inframammary fold and at the inferior breast contour.

FIGURE 3: RAINBOW SCALE FOR ANTERIOR-POSTERIOR ASSESSMENT

FIGURE 4: RAINBOW SCALE FOR LATERAL ASSESSMENT

MEDICAL Apyx Medical Corporation	
Protocol Number: APX-22-03	Effective Date: 23SEP2022 Revision No: 2.0
Title: Minimally Invasive Breast Lift Procedure Litilizing the Renuvion APR System	

FIGURE 5: RAINBOW SCALE FOR OBLIQUE ASSESSMENT

#### 4.3.3.8 MORPHOMETRIC BREAST MEASUREMENTS

Morphometric measurements of breast will be conducted at baseline and 30 Days, 90 Days, and 180 Days post procedure as shown in Figure 8. Points of measurement will include:

- Suprasternal notch to nipple distance (SNN-N): measurements taken at the mid nipple diameter on both • sides.
- Inframammary crease to nipple distance (IMC-N): measurement taken from the base of the breast to the base of the nipple.
- Midclavicular line to nipple distance (*MCL-N*): measurement taken from the mid clavicle to the mid nipple.
- Nipple to nipple distance (N-N): measurements taken at the mid nipple diameter on both sides.
- SSN-IMC: vertical distance from the suprasternal notch to the inframammary crease.
- SSN-base: vertical distance from the suprasternal notch to the lowest point on the base. •
- PROJ: maximum point of breast projection measured perpendicular to the chest wall.
- NAC: nipple-areola complex diameter.

FIGURE 6: MORPHOMETRIC MEASUREMENTS

MEDICAL Apyx Medical Corporation	
Protocol Number: APX-22-03 Effective Date: 23SEP2022 Revision No: 2.0	
Title: Minimally Invasive Breast Lift Procedure Utilizing the Renuvion APR System	

#### 4.3.3.9 ASA PHYSICAL STATUS CLASSIFICATION SYSTEM

The ASA Physical Status Classification System has been in use for over 60 years. The purpose of the system is to assess and communicate a patient's pre-anesthesia medical co-morbidities. The classification system alone does not predict the perioperative risks, but used with other factors (e.g., type of surgery, frailty, level of deconditioning), it can be helpful in predicting perioperative risks, see **Table 5**.

#### TABLE 5: ASA PS CLASSIFICATION

ASA PS Classification	Definition	Adult Examples, Including, but not Limited to:
ASA I	A normal healthy patient	Healthy, nonsmoking, no or minimal alcohol use.
ASA II	A patient with mild systemic disease	Mild diseases only without substantive functional limitations. Current smoker, social alcohol drinker, pregnancy, obesity (30 <bmi<40), disease.<="" dm="" htn,="" lung="" mild="" td="" well-controlled=""></bmi<40),>
ASA III	A patient with severe systemic disease	Substantive functional limitations; One or more moderate to severe diseases. Poorly controlled DM or HTN, COPD, morbid obesity (BMI ≥40), active hepatitis, alcohol dependence or abuse, implanted pacemaker, moderate reduction of ejection fraction, ESRD undergoing regularly scheduled dialysis, history (>3 months) of MI, CVA, TIA, or CAD/stents.
ASA IV	A patient with severe systemic disease that is a constant threat to life	Recent (<3 months) MI, CVA, TIA or CAD/stents, ongoing cardiac ischemia or severe valve dysfunction, severe reduction of ejection fraction, shock, sepsis, DIC, ARD or ESRD not undergoing regularly scheduled dialysis.
ASA V	A moribund patient who is not expected to survive without the operation	Ruptured abdominal/thoracic aneurysm, massive trauma, intracranial bleed with mass effect, ischemic bowel in the face of significant cardiac pathology or multiple organ/system dysfunction.
ASA VI	A declared braindead patient whose organs	(Intentionally left blank)

